## Procedure

In order to recruit the participants, gyms and football clubs across South-Lebanon and Damascus-Syria were visited and information sheets were distributed. These sheets, (1) explained the study purpose, (2) stressed on the voluntary participation and the free will to withdraw from the study, (3) described the experiment process and its duration; (5) stated possible risks and benefits, (6) stressed over confidentiality and (7) provided investigators contact methods.

To start with the experiment, each enrolled participant signed a consent form. Then, an independent examiner who was not involved in the enrollment process had systematically allocated participants into one of the three intervention groups, by withdrawing names randomly out of a bowl. The first draw was assigned to the static stretching group; the second draw assigned to the dynamic stretching group; the third draw assigned to the DTFM group, and so on. In addition, the investigator who entered eligible participants in the study was not aware of which group they were allocated.

The experiment took place in July 2017, over a four weeks period, and participants in each group followed their intervention protocol three times a week, for a total of 12 sessions.

**Static stretching group.** Static stretching was chosen for its effectiveness in increasing both acute and chronic extensibility. All participants laid on the floor in a supine position with both feet pointing upwards. The tested limb was in full knee extension and the foot in a relaxed position and was moved up passively to a point of slight pain or discomfort at the posterior aspect of the thigh. This technique puts the

hamstrings muscle at its greatest possible length. According to the American College of Sports Medicine (ACSM), this position should be held for 30 seconds and was performed three times for a total of one minute and 30 seconds, 15 minutes after a match or training. The contralateral leg was stabilized by means of another collaborator in order to prevent compensation by rotation or elevation of the pelvis.

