## **Data Collection Methods**

Measurements took place on three occasions, (1) baseline, on the first session; (2) 15 minutes, after the first intervention (acute phase); and (3) after four weeks (chronic phase). In addition, (1) age, (2) height, (3) weight and (4) and injury occurrence rate was recorded for each footballer. On the other hand, flexibility, agility and maximal

voluntary muscle strength measures were taken in the same manner and time for all participants across groups.

[figure not shown]
All measurements were taken by one assessor who didn't know at the time of testing to what group the data belonged to. In addition, this assessor was not involved in the implementation of any of the techniques in this study.

**Flexibility.** Extensibility of the hamstrings muscle represented knee flexibility.

Hamstrings muscle injury is common in sports requiring running. It is usually, the result of a muscle imbalance where the quadriceps muscle is strong and hamstrings are weak and inflexible, what puts a great deal of pressure on the hamstrings leading to injury and strain. Straight leg raise (SLR) is a widely used outcome measure used to assess the extensibility of the hamstrings muscle, where its high reliability makes it an easy and reliable method ICCs of 0.96, and high SEM values (2.2°) and MDD (6°). SLR was first applied to all participants across the groups. All football players laid supine and taught to relax during testing. The tested limb was raised by a volunteer therapist with the knee in full extension and the foot in a relaxed position. The other lower limb was stabilized in a neutral hip rotation and full knee extension by another volunteer. The test was stopped once the therapist felt a strong resistance, or when the pelvic rotation was noted. Then, the assessor placed the goniometer over the greater trochanter, with one arm aligning the lateral femoral condyle, and the other arm aligning parallel to the ground, in a direction to the mid-axillary line and recorded the hip angle. The scores were recorded as degrees of range of movement.

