## **Data Analysis**

Data were analyzed using the Statistical Package for the Social Sciences (SPSS) version 21.0 for Windows. Descriptive statistics (mean, standard deviation) were calculated to characterize participants' age, weight, and height. Means of the main key variables of the study were also calculated. The Shapiro-Wilk test was used to check the normality of the data distribution. A probability (p) value of  $>0.05$  means that there was no significant difference between groups.

To check for any difference in the incidence of muscle injury between each of the intervention groups, Fisher exact test was used because expected cell count was less than 5.

Dependent t-tests were used to determine any significant differences between the acute and chronic phases of extensibility, agility and muscle strength, and to check the difference between the baseline and chronic phases of these dependent variables.

Analysis of variance (ANOVA) test was used to check for any significant difference between the interventions groups and each of the extensibility, agility, and strength. This test was repeated for three different phases (baseline, acute and chronic). Moreover, after a statistically significant difference was shown between the variables, Tukey's Post Hoc test was used to show where the differences occurred between intervention groups.

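### The acute and chronic comparisons between techniques ignore each player's own baseline score, which gives away precision at no saving

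*Combined protocol and SAP*

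**What the plan says.** The Data Collection Methods section provides a pre-treatment value of each continuous outcome: "Measurements took place on three occasions, (1) baseline, on the first session". The later measurements are 15 minutes after the first intervention (acute) and after four weeks (chronic).

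The Data Analysis section gives one method for comparing arms on these outcomes: "Analysis of variance (ANOVA) test was used to check for any significant difference between the interventions groups and each of the extensibility, agility, and strength". It continues: "This test was repeated for three different phases (baseline, acute and chronic". When a result is significant, "Tukey's Post Hoc test was used to show where the differences occurred between intervention groups". No covariate, change score, repeated-measures model or mixed model is named.

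Baseline is used in two places only: its own ANOVA, and dependent t-tests, among them one "to check the difference between the baseline and chronic phases of these dependent variables". Injury is compared separately by Fisher's exact test and is not part of this point.

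Under Procedure, players are allocated to three groups "by withdrawing names randomly out of a bowl", the draws being assigned to the groups in rotation.

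**The concern.** The trial asks which technique does better, so the comparison between arms is the one that answers it. Players differ from one another in hamstring extensibility, agility and strength before any treatment. Part of that difference persists to follow-up, and an ANOVA of raw follow-up scores leaves it in the error term although the variable that would remove it has been recorded.

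Neither existing use of baseline repairs this. The dependent t-tests compare phases within players and say nothing about one arm against another. The baseline ANOVA can show a chance gap but does not correct the later comparisons for it.

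The consequence is wider intervals and a greater chance of missing a real difference. This matters more because the plan reads p > 0.05 as no significant difference between groups and mentions no confidence intervals, so an imprecise null result could be taken as evidence that the techniques are equivalent.

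**Working it through.** The available text gives no sample size, power or target difference, so there is no design figure to reproduce. The sample size may be in text not available for review, and its absence is not held against the plan.

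**Inputs from the documents (Data Collection Methods, Flexibility).** Straight leg raise (SLR): ICC 0.96, SEM 2.2 degrees, MDD 6 degrees.
- These agree with one another: 1.96 × √2 × 2.2 = 6.1 degrees, against the stated 6.
- Implied between-player SD: SEM/√(1-ICC) = 2.2/√0.04 = 11.0 degrees.

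**Assumptions.** Arm sizes of 15, 20 and 30; r from 0.3 to 0.9; one arm better than the other two by 6 degrees; equal variance at baseline and follow-up. The cited ICCs (0.96 for SLR, 0.95 for the T-Drill, 0.983 for 1RM) are test-retest values. They make a substantial r plausible, especially over 15 minutes, but do not fix it over four weeks of intervention.

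**General result, any of the three outcomes.** The residual variance with baseline adjustment, relative to without, is 1-r². The equivalent multiplication of sample size is 1/(1-r²).

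| r | 1-r² | 1/(1-r²) |
|---|---|---|
| 0.3 | 0.91 | 1.10 |
| 0.5 | 0.75 | 1.33 |
| 0.7 | 0.51 | 1.96 |
| 0.8 | 0.36 | 2.78 |
| 0.9 | 0.19 | 5.26 |

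**Power for SLR.** Noncentral F, three arms, means (0, 0, 6), grand mean 2, alpha 0.05. The noncentrality is n(4 + 4 + 16)/[121(1-r²)], with r = 0 for the unadjusted test. Error degrees of freedom are 3n-3 unadjusted and 3n-4 adjusted. For example, at n = 20 it is 480/121 = 3.97 unadjusted and 480/(121 × 0.51) = 7.78 at r = 0.7.

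| n per arm | Unadjusted | r = 0.3 | 0.5 | 0.7 | 0.8 | 0.9 |
|---|---|---|---|---|---|---|
| 15 | 30% | 32% | 39% | 54% | 70% | 94% |
| 20 | 39% | 43% | 51% | 68% | 83% | 98% |
| 30 | 56% | 61% | 70% | 86% | 96% | >99% |

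**Tukey 95% half-width for SLR, 20 per arm.** q(0.95; 3, df) × 11 × √(1-r²)/√20, ignoring the small extra variance from baseline imbalance. Unadjusted it is 8.4 degrees. At r = 0.3, 0.5, 0.7, 0.8 and 0.9 it is 8.0, 7.2, 6.0, 5.0 and 3.7 degrees. The unadjusted half-width is larger than the cited 6-degree MDD.

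**Error rates under no effect.** 60,000 simulated trials per setting, with bivariate normal baseline and follow-up.
- Overall, the unadjusted ANOVA rejects in 4.8% to 5.1% of trials, so it is valid.
- Some pair of arms differs at baseline by at least 0.5 SD in 36%, 25% and 13% of trials at 15, 20 and 30 per arm.
- Given such a gap at 20 per arm, the ANOVA rejects in 7%, 9%, 14% and 18% of trials at r = 0.3, 0.5, 0.7 and 0.9.
- In the other roughly 75% of trials at 20 per arm, a separate run gives 4.2%, 3.5%, 2.0% and 0.3%. The two parts average back to about 5%; at r = 0.7, 0.25 × 13.9% + 0.75 × 2.0% = 5.0%.
- ANCOVA stays at about 5% given such a gap (4.7% to 5.3% across settings).

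**The case against.** The strongest reply is that this is a choice of efficiency and not an error. Under a random draw, a one-way ANOVA with Tukey comparisons at follow-up is a valid test. That is correct, and no bias or overall inflation of type I error is claimed. The raised rates after a baseline gap must be read with the lowered rates when there is none, and the 0.5 SD cut-off is a choice made for illustration.

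The second reply is that the loss in this trial is not established. The documents give no r, trial SD or target difference, and the available text gives no arm size. The SD of 11 comes from cited reliability figures, and the players in that source may differ from these. The 6 degrees is a measurement-error threshold, not a planned difference between arms. At 20 per arm, adjusted power runs from 43% to 98%, and at r = 0.3 the gain is only 4 percentage points. This stands as a limit on the size. It does not reverse the direction: adjustment gained power at every r tried, after paying one degree of freedom.

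The third reply is that the experiment is dated July 2017 and the analysis is described in the past tense, so a live plan may no longer exist to correct. That changes how the adjusted analysis should be labelled, not whether it is worth doing.

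**Conclusion.** The point holds. Baseline scores are collected for all three continuous outcomes, and no acute or chronic comparison between arms uses them. The existing ANOVA is valid but avoidably weak.

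The omission is certain from the text; its size depends on r. At r around 0.3 little is lost. At r = 0.7, leaving baseline out costs about half the effective sample (1-r² = 0.51), and more above that. The SLR figures also rest on the implied SD of 11 degrees, the assumed 6-degree difference and the assumed arm sizes. No absolute illustration is possible for agility or strength, because the documents give no SD or SEM for the study's T-Drill or 1RM scores. This is a change that should be made, not a flaw that invalidates the trial.

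**What to change.** Replace the acute and chronic ANOVAs with an ANCOVA of the follow-up score on arm and the same outcome's baseline value, one model per outcome and phase. Report Tukey-adjusted pairwise differences in adjusted means with 95% confidence intervals, and check linearity and common slopes.

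An ANOVA of change scores is not an equal substitute. With equal variances, its error variance relative to the raw-score ANOVA is 2(1-r): 1.4 at r = 0.3, 1.0 at 0.5 and 0.6 at 0.7, against 0.91, 0.75 and 0.51 for ANCOVA.

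If one model per outcome is preferred, use a mixed model with only the two post-baseline phases as response. Its terms would be arm, phase, arm-by-phase, baseline and baseline-by-phase, with an unstructured covariance for a player's two follow-up values. The simple ANCOVA is enough to settle this point. The baseline table can then be descriptive, since the baseline ANOVA corrects nothing.

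The cost is one degree of freedom per ANCOVA and a modest reanalysis in SPSS, with no new data. If the data have already been analysed, label the adjusted analysis post hoc and show it beside the original ANOVA.

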**Agility.** Agility was chosen to represent the footballer's performance. This athletic event involves elements of speed, change of direction, and varying types of movement. After the measurement of the extensibility, agility was measured by the T-Drill test. The T-Drill has been proven to be a highly reliable testing measurement, ICC (0.95 with 95 % confidence interval). Footballers were instructed on how to perform the T-Drill and on the test procedures. Then, they were instructed to jog for 2 min to warm-up. The participants performed the T-drill twice and the trial with the best time was taken for analysis by the mean of an alert assessor with a stopwatch. Results were measured in seconds and scores were interpreted as (1) excellent, < 9.5; (2) good, 9.5-10.5; (3) average, 10.5-11.5; and (4) poor, > 11.5. A diagram of the T-Drill with its dimensions are shown in (Figure 2).

**FIGURE 2.** Diagram of T-Drill procedure.

**Strength.** Finally, maximal voluntary muscle strength was measured by one repetition maximum (1RM) tests. The ICC for 1-RM test-retest measures was (0.983, 95% confidence interval= 0.964–0.997. After a rest time of 5 min, participants were

guided to the knee flexors strengthening machine (hamstrings curl machine).

Resistance was placed just proximal to the posterior part of the calcaneus bone.

Footballers performed first specific warm-up, consisting of a set of ten repetitions of knee flexion, with a light load. Afterwards, for safety reasons, an estimation of hamstring 1RM was calculated using Brzycki formula [Weight lifted  $\div$  (1.0278 - (0.0278  $\times$  Number of repetitions)]. This formula exhibited a relatively low level of bias (1.6 to 0 kg) and had an ICC above 0.97 and the lower end of the 95% confidence interval was above 0.94.

Maximal voluntary strength was recorded in kilograms.

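### The chronic-phase tests use only players with a chronic score, so any player untestable through injury would drop out because of an outcome the arms are compared on; the plan has no rule for this case

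*Combined protocol and SAP*

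**What the plan says.** All references are to the combined protocol and SAP.

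- **Allocation and follow-up (Procedure).** Names are drawn in sequence into three arms ("The first draw was assigned to the static stretching group; the second draw assigned to the dynamic stretching group", then the massage group), so the arms are about equal. Over four weeks, "participants in each group followed their intervention protocol three times a week, for a total of 12 sessions".
- **Measurement times (Data Collection Methods).** Baseline and the acute measurement both belong to the first session. The third measurement comes "after four weeks (chronic phase").
- **Injury (Data Collection Methods; Data Analysis).** "injury occurrence rate was recorded for each footballer", listed beside age, height and weight, with no recording window or definition. It is then an outcome: "To check for any difference in the incidence of muscle injury between each of the intervention groups, Fisher exact test was used", chosen because the expected cell count was below 5.
- **Performance tests (Data Collection Methods, Agility and Strength).** Agility is the better of two timed T-Drill runs. On strength: "Finally, maximal voluntary muscle strength was measured by one repetition maximum (1RM) tests". The same paragraph then says that hamstring 1RM was estimated on safety grounds by the Brzycki formula, from load and repetitions on a hamstring curl machine.
- **Analysis (Data Analysis).** Arms are compared by ANOVA, and "This test was repeated for three different phases (baseline, acute and chronic"). Paired t-tests compare acute with chronic and baseline with chronic.

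The text gives no analysis set, no missing-data method and no rule for a player who cannot do a test.

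**The concern.** The T-Drill and the hamstring curl load the muscle whose injury is being counted. A player with a recent muscle injury may be unable to do them at week four. The chronic ANOVA and both paired t-tests would then omit that player, while the baseline and acute ANOVAs would keep him. The phases would compare different people, and the reason for leaving would be an outcome that the arms are compared on.

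If untestable players would have scored worse than the rest, and there are more of them in one arm, that arm's chronic mean is flattered. Performance and injury are read together to judge the techniques, so the arm that does worse on injury could look better on agility and strength.

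**Working it through.** **1. Nothing to reproduce.** The text read for this review gives no sample size, injury count, dropout rate or number tested per phase. Everything in steps 3 to 5 therefore rests on assumed inputs.

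**2. What Fisher's test tells us.** With three equal arms, and injury the rarer category, the expected injuries per arm are total / 3. Requiring total / 3 < 5 gives total < 15, so at most 14. This is a ceiling only; one injury in the whole trial would also satisfy it.

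**3. Size of the shift.** Let p be the share of an arm that is untestable at week four because of injury, and d the shortfall of those players in SD units. With no other arm effect, the contrast A minus C over all allocated players is −(p_A − p_C) × d, and the tested-only contrast is 0. The shift in favour of A is

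(p_A − p_C) × d.

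- Assumed 15% v 0%, or 20% v 5%: the difference is 0.15 either way.
- d = 0.5: 0.15 × 0.5 = 0.075 SD.
- d = 1: 0.15 × 1 = 0.15 SD.
- p_A = p_C, or d = 0, or no injured non-testers: 0.

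For scale, the standard error of a two-arm contrast in SD units is √(2/n): 0.37, 0.32 and 0.26 at n = 15, 20 and 30 per arm (assumed). The largest ratio is 0.15 / 0.26, or about 0.6 of a standard error.

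A more extreme case is 4 untestable players in one arm and none in the others. At d = 1 the shift is 4/10 = 0.40 SD, 4/20 = 0.20 SD or 4/30 = 0.13 SD. At d = 2, a simulated three-arm ANOVA at 0.05 (3,000 runs per scenario) gave:

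| n per arm | Rejects, tested only | Rejects, all players kept |
|---|---|---|
| 10 | 5.9% | 27% |
| 20 | 4.8% | 15% |
| 30 | 5.1% | 12% |

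The tested-only analysis does not see the injured arm's shortfall. With 2 untestable players in every arm, the shift between arms was zero.

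**4. Does a mixed model recover it?** Baseline and acute scores both come from the first session, before any later injury. A model of arm, phase and arm by phase therefore predicts an uninjured course for the missing player. In simulation of the step 3 shares and shortfalls (n = 15, 20, 30; correlation 0.8 between phases, assumed), the contrast with all players kept was about −0.06 to −0.16 SD. The tested-only contrast was within ±0.01 SD, and so was the likelihood estimate equivalent to the mixed model. It recovers nothing of this bias.

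**5. What the mixed model does give.** At n = 20 per arm and correlation 0.8, the SD of a chronic-only contrast is √(2/20) = 0.32. For a contrast in change from baseline it is √(2 × (1 − 0.8)) × 0.32 = 0.63 × 0.32 = 0.20. Simulation with baseline adjustment agreed (about 0.33 falling to 0.20). This gain is separate from the injury question.

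**The case against.** - **No injured non-tester is shown.** A reader might infer that injured players were in fact dropped. No section says so. Data Collection Methods says the measurements followed one procedure and schedule in every group. That describes uniformity, not completeness, but it points away from selective testing. A figure in that section was not available in the text read, so counts by phase may exist. This objection stands and makes the point conditional.
- **The injury premise is thin.** Using Fisher's test does not show that injuries were many, that they arose within the four weeks, or that they were hamstring injuries. This stands. Comparing incidence between intervention groups does suggest follow-up rather than history, but the window is not stated.
- **The strength test is not necessarily a maximal lift.** A reader who stops at the first sentence of the Strength paragraph might assume so. An estimate from repetitions may be feasible for some injured players. This weakens the argument for 1RM; it does not touch the T-Drill.
- **Only the untestable matter.** Injured players who recovered, or who tested and scored badly, stay in, so injury share overstates the relevant share. This is correct.
- **Injury is already reported separately, and worst-rank scoring counts it twice.** Fisher's test would show excess injuries to the extent its power allows. Whether performance should also reflect them is a choice of estimand. That is a reason to make worst-rank a sensitivity analysis and not the main one.

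**Conclusion.** The point holds as a conditional gap. Injury is a compared outcome, the chronic ANOVA and the paired t-tests need a chronic score, and no rule covers a player who cannot be tested. The direction, in favour of the arm with more injuries, requires three things: players untestable because of injury in the four weeks, unequal numbers of them by arm, and worse underlying performance in those players.

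The size cannot be derived from the documents. It is about 0.07 to 0.15 SD under the assumed 15-point difference and a shortfall of 0.5 to 1 SD. That is at most about 0.6 of a standard error at 15 to 30 players per arm. It is larger in the extreme small-arm cases and zero if every injured player was tested.

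Two stronger readings are not supported: that the chronic results are biased, and that a mixed model would correct them if they were.

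**What to change.** 1. State that all allocated players are analysed in the arm drawn. Tabulate the number tested by arm and phase, with the reason for each missing score, and keep untested players in the injury table. State the injury recording window. If the table shows no injured non-testers, the question is closed.
2. Add a sensitivity analysis for chronic T-Drill and 1RM: players untestable because of muscle injury share the worst rank (slowest time, lowest load), and the arms are compared by Kruskal-Wallis. The cost is a composite with no unit in seconds or kilograms that counts the same injury in two outcomes.
3. On separate grounds, replace the phase-by-phase ANOVAs and the within-arm paired tests with one mixed model per outcome (arm, phase, arm by phase). It uses the baseline already collected and compares change between arms directly. Do not present it as a remedy for injury-related missing scores.

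No new test data are needed. The work is analysis wording, one SPSS MIXED run per outcome, two rank tests and one table.

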**Dynamic stretching group.** The dynamic stretching technique was included for its positive effects on agility and muscle strength. Participants in this group, swung their tested leg actively into hip flexion while keeping their knee fully extended and their ankle fully plantar flexed, until a stretch was felt in the posterior thigh. This was repeated over 30 seconds and included in the participant's warm-up phase.

**Deep transverse friction massage group.** Participants were taught by one of the examiners how to sit and perform pre-exercise self-massages on their tested leg MTJ. The procedure consisted of applying friction massage by fingertips transversely to the hamstrings tendon, in a sitting position. The tendon was located over four finger widths proximal to the medial and lateral epicondyles of the femur. One examiner carefully monitored how the technique was performed to assure the precision of the application. This massage technique was applied over a duration of 30 seconds.

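### At the acute phase the plan implies that only the static arm has a completed match or training behind it, so its acute contrasts mix technique with exercise state

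*Combined protocol and SAP*

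**What the plan says.** The combined protocol and SAP places the three interventions differently around exercise (Procedure):

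- Static stretching "was performed three times for a total of one minute and 30 seconds, 15 minutes after a match or training".
- Dynamic stretching: "This was repeated over 30 seconds and included in the participant's warm-up phase".
- DTFM: players were taught to "perform pre-exercise self-massages on their tested leg MTJ".

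Players "followed their intervention protocol three times a week, for a total of 12 sessions".

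Data Collection Methods puts the acute measurement at "15 minutes, after the first intervention (acute phase"). Baseline is placed only at the first session, with no statement of whether it came before or after exercise. The same section says that flexibility, agility and "voluntary muscle strength measures were taken in the same manner and time for all participants across groups".

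Data Analysis runs a between-group ANOVA on extensibility, agility and strength: "This test was repeated for three different phases (baseline, acute and chronic"). Tukey's test follows a significant result. Dependent t-tests compare acute with chronic values and baseline with chronic values. No baseline covariate, change score or adjustment for exercise state is described for the between-group tests.

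**The concern.** The acute clock starts at the intervention, and the interventions sit on opposite sides of the exercise bout. If the text is followed, static players reach the acute straight leg raise (SLR), T-Drill and strength tests after a completed match or training session. Dynamic and DTFM players reach them after a warm-up component or a pre-exercise massage.

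A match or training session may itself change extensibility, agility and strength, through fatigue or through residual warming. If none of the techniques had any acute effect, static could still differ from the other arms by whatever the bout does. A true acute effect could equally be masked. Randomisation and the blinded assessor do not help, because the schedule creates the difference after allocation.

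The acute ANOVA with Tukey is the plan's only between-arm test of acute effects, so the reading of static's acute result depends on this.

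**Working it through.** **Step 1. Timeline implied by the text**

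| Arm | Placement (Procedure) | State at the acute measure |
|---|---|---|
| Static | 15 min after a match or training | Bout completed |
| Dynamic | Within the warm-up | 15 min after a warm-up component; bout not completed |
| DTFM | Before exercise | 15 min after the massage; bout not completed |

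For static, the time from the end of the bout to the acute measure is 15 min (wait) + 3 × 30 s = 1.5 min (stretch) + 15 min (wait) = 31.5 min. This is a minimum, because rests between repetitions are not stated. The entries for the other two arms are inferred. The text does not say whether those players had begun exercising by then, but a bout would have to last under 15 min to be complete.

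**Step 2. Analyses touched**

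- Acute ANOVAs: 3 (one per outcome).
- Acute Tukey contrasts involving static: 2 of 3 pairs × 3 outcomes = 6 of 9.
- Acute-versus-chronic paired t-tests: static's values in all 3.
- Baseline ANOVAs: also affected if static's baseline was taken in the 15-minute gap after the bout.

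**Step 3. Illustration of size (SLR)**

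The plan gives no sample size, effect size or power, so there is no figure of its own to reproduce. Its only usable inputs are the cited reliability values: "ICCs of 0.96, and high SEM values (2.2°) and MDD (6" degrees).

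- Check: MDD = 1.96 × √2 × 2.2 = 6.1°, in line with the quoted 6°.
- Implied SD = SEM/√(1 − ICC) = 2.2/√0.04 = 11.0°.

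Assumed, not in the documents: equal arms of n = 10 to 40; this SD applies to the trial's players; no technique effect; a bout-only shift of d SDs in static alone. The true means are then (d, 0, 0). The ANOVA rejection rate comes from the noncentral F distribution with df 2 and 3n − 3, λ = n × (2/3) × d², α = 0.05. For example, with n = 20 and 6°, d = 6/11 = 0.545 and λ = 20 × (2/3) × (6/11)² = 3.97, which gives 0.394.

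| Shift in static | n = 10 | n = 20 | n = 30 | n = 40 |
|---|---|---|---|---|
| None | 0.050 | 0.050 | 0.050 | 0.050 |
| 2.2° (d = 0.20) | 0.068 | 0.090 | 0.113 | 0.136 |
| 5.5° (d = 0.50) | 0.178 | 0.337 | 0.489 | 0.621 |
| 6° (d = 0.545) | 0.204 | 0.394 | 0.565 | 0.702 |

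By simulation (100,000 runs per cell), the probability that the ANOVA is significant and Tukey flags at least one static contrast at 6° is 0.183, 0.371, 0.540 and 0.680. With no shift it is about 0.03.

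The d = 0.50 row applies to any of the three outcomes. The 6° row uses the MDD only as a convenient scale. It is a measurement-error threshold, and nothing in the documents says that a bout moves SLR by that much.

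**The case against.** **Exercise state is inferred.** A reader might conclude that static was in fact measured after a bout and the other arms before one. The documents do not establish that. No section states exercise state at any measurement, and the first-session sequence is put together from a general description of each regimen and the anchor of the acute measure. This stands: the point is about what the plan implies.

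**The same-time sentence.** Data Collection Methods says measures were taken in the same manner and time across groups. The most natural reading is the same listed occasions, the acute one being 15 minutes after the intervention. That reading does not equalise exercise state. A reading that did would conflict with the placements under Procedure. A figure after this sentence is not available to us, so nothing is inferred from it.

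**Placement is part of the regimen.** Static stretching is defined as post-exercise, so static versus another arm is a legitimate randomised comparison of regimen plus placement. This also stands. It limits what the contrast can claim but does not make the test invalid, and the rejection rates above are errors only if the question is the technique's own effect.

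**Test-day preparation.** All arms jog for 2 minutes before the T-Drill, rest 5 minutes before the strength test and do a ten-repetition specific warm-up. This partly evens out residual warming for agility and strength. It does nothing for SLR, which is tested first, or for fatigue.

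**The numbers are illustrative.** Agreed. They run from near nominal to 70% depending on assumed inputs, and the SD comes from a cited reliability source.

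**Conclusion.** The concern holds in a limited form. As written, the plan ties a completed bout to the static arm at the acute phase, and the unadjusted ANOVA and Tukey tests cannot separate that from the technique. Six of nine acute Tukey contrasts, and static's part in three acute-versus-chronic t-tests, cannot be read as effects of the technique or of time alone. The size and direction of the bias are unknown. Rejection rates of 7% to 14% (2.2° shift) and 20% to 70% (6° shift) show only that the problem could range from small to large, under assumed arm sizes, SD and shift.

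A reader might also infer that the static acute contrasts must be deleted, or that the whole trial is compromised. Neither follows. The contrasts remain usable as regimen-plus-placement comparisons. Dynamic versus DTFM is not exposed to this before-or-after-bout difference. The injury comparison is unaffected. The four-week comparison is not undermined by the acute schedule, but exercise state at four weeks is also unstated, so it stands only if that state was the same in all arms.

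**What to change.** **For a repeat of the study.** At session 1, give every arm its intervention and take baseline and acute measures in the same exercise state, with no bout before either. Use the post-exercise placement for static from session 2 onward. This changes the schedule of one session out of 12.

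**For data already collected**, in Data Analysis:

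1. State, by arm, whether the baseline and acute measures came before or after that day's match or training. If no bout preceded static's measures, keep the acute ANOVA as planned.
2. If static's acute measure followed a bout, or this cannot be ruled out, report its acute contrasts as regimen-plus-placement comparisons with no claim about the technique. Treat dynamic versus DTFM as the interpretable acute contrast.
3. In that case, do not read static's acute-versus-chronic t-test as a time effect.
4. If baseline and acute measures were taken in the same exercise state within each arm, a baseline-adjusted (ANCOVA) acute comparison may be used. It would remove much of the shift, though not necessarily all of it.
5. Keep the four-week ANOVA and the Fisher test, on the condition that the four-week measures were taken in the same exercise state in all arms. Say whether they were.

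**Cost.** No new measurements and no arm dropped. The work needs first-session and four-week timing, which the text does not show was recorded. The price is a weaker conclusion, or none, about static's acute effect relative to the other arms.
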